14.4 Secondary Objectives

To evaluate the effectiveness of IC2000/SPY and Tc99m/Gamma Probe in the identification of at least one lymph node (histology confirmed lymph node) per subject, the proportion of subjects with at least one lymph node identified with IC2000/SPY *invivo* and confirmed by histology (\mathbf{Q}_{T}) and the proportion of subjects with at least 1 lymph node identified with Tc99m/Gamma Probe and confirmed as lymphoid tissue (\mathbf{Q}_{C}) will be described using summary statistics. The denominator for both \mathbf{Q}_{T} and \mathbf{Q}_{C} will be the number of subjects where mapping was attempted.

In a secondary analysis, the mITT population will be used instead of the PP population.

To evaluate the effectiveness of IC2000/SPY as an intraoperative fluorescence visualization tool in delineation and mapping of lymphatic vessels in the identification of lymph nodes (histology confirmed lymph nodes), the proportion of lymph nodes identified by IC2000/SPY (histology confirmed lymph nodes) by following a fluorescent lymphatic vessel and the proportion of lymph nodes identified by IC2000 and SPY (histology confirmed lymph nodes) with no lymphatic vessels visible by IC2000/SPY will be described using summary statistics. Denominator will be the total number of lymph nodes

identified by any method (histology confirmed). The concordance rate and the findings of discordant lymph nodes will also be presented.

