2.6 Study Variables

Primary Variable

- To assess the effectiveness of IC2000 and SPY-PHI (SPY Portable Handheld Imager; also called "IC2000 and SPY") Fluorescence Imaging System in the identification of lymph nodes (histology confirmed lymph nodes), during lymphatic mapping and sentinel lymph node biopsy in subjects with early stage breast cancer.
 - Defined as the proportion of lymph nodes identified and excised by IC2000/SPY compared to the proportion of lymph nodes identified and excised by Tc99m/Gamma Probe, (histology confirmed lymph nodes). Denominator is the total number of lymph nodes identified and excised, inclusive of clinically suspicious lymph nodes (histology confirmed).

Secondary Variables

- To evaluate the effectiveness of IC2000/SPY and Tc99m/Gamma Probe in the identification of at least one lymph node (histology confirmed lymph node) per subject.
 - Defined as the proportion of subjects in which at least one lymph node is identified by IC2000/SPY, and Tc99m/Gamma Probe, (histology confirmed lymph nodes). Numerator is the number of subjects who have at least one lymph node identified by IC2000/SPY, and the number of subjects who have at least one lymph node identified by Tc99/Gamma Probe, respectively (histology confirmed). Denominator is the total number of subjects where mapping was attempted.
- To evaluate the effectiveness of IC2000 and SPY as an intraoperative fluorescence visualization tool in delineation and mapping of lymphatic vessels in the identification of lymph nodes (histology confirmed lymph nodes).
 - Defined as the proportion of lymph nodes identified by IC2000 and SPY (histology confirmed lymph nodes) by following a fluorescent lymphatic vessel compared to the proportion of lymph nodes identified by IC2000 and SPY (histology confirmed lymph nodes) with no lymphatic vessels visible by IC2000 and SPY. Denominator is the total number of lymph nodes identified by any method (histology confirmed).
- To confirm the safety of intradermal injection of IC2000 in intraoperative delineation and mapping lymphatic vessels and identification of lymph nodes.
 - Defined by the incidence of adverse events with IC2000.

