13.5 Reporting of Technical Complaints / Device Deficiencies

13.6 ADEs Technical Complaints / Device Deficiencies that are UADEs

14. STATISTICAL CONSIDERATIONS

14.1 Analysis PopulationsPer-protocol (PP)

Since this is a non-inferiority design, the PP analysis population will be primary; it will comprise all subjects that: (1) meet all eligibility criteria; (2) received the full dose of tracer / dye; (3) successfully completed the mapping procedure (i.e. have at least one lymph nodes detected *in-vivo* by IC2000 and SPY or by Tc99m and Gamma Probe, or have lymph nodes deemed clinically suspicious), and; (4) have histology confirmed lymph nodes.

Modified Intent to treat (mITT)

The mITT analysis population will comprise all enrolled subjects who received at least one injection of IC2000 and Tc99. All subjects meeting this criterion will be included in the mITT population regardless of whether or not (1) they received lymphatic mapping (i.e. they only had LNs identified through palpation), or (2) received the full dose of tracer / dye. Subjects who have the mapping procedure aborted due to circumstances, such as a higher stage cancer than initially expected, subjects with failed mapping, or subjects without histology confirmed lymph nodes will not be included in the mITT. The mITT population will be used for a secondary analysis of the primary endpoint.

Safety

The safety analysis population will comprise all subjects enrolled in the study who received at least one injection of IC2000 regardless of whether LN mapping was initiated or was successful. All safety endpoints, including the summary of AEs or ADEs in the trial, will be analyzed using this analysis population.

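### The per-subject detection rate is defined over all subjects with mapping attempted, but the populations named in 14.4 both leave out subjects in whom no node was found

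*Combined protocol and SAP*

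**What the plan says.** Section 2.6 defines the per-subject endpoint and states: "Denominator is the total number of subjects where mapping was attempted". Section 14.4 repeats this for both methods: the denominator "will be the number of subjects where mapping was attempted". The numerator counts subjects with at least one node found by the method and confirmed by histology. The rates are to be described with summary statistics.

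Directly below, 14.4 adds: "In a secondary analysis, the mITT population will be used instead of the PP population". No sentence assigns PP to this endpoint outright. It is implied here, and 14.1 calls PP the primary population in general terms.

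Section 14.1 defines the two sets:

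- PP subjects must "meet all eligibility criteria; (2) received the full dose of tracer / dye", must have completed mapping successfully (a node found in vivo by either method, or clinically suspicious nodes), and must have histology-confirmed nodes.
- mITT takes subjects injected with both agents, "regardless of whether or not (1) they received lymphatic mapping (i.e. they only had LNs identified through palpation"). It leaves out "Subjects who have the mapping procedure aborted due to circumstances", and "subjects with failed mapping, or subjects without histology confirmed lymph nodes will not be included in the mITT".
- On the purpose of mITT, 14.1 says: "The mITT population will be used for a secondary analysis of the primary endpoint".

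Section 12.3 defines failed mapping as no node by either method and none clinically suspicious. Section 2.7 requires failed mapping to be documented.

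**The concern.** An analyst can follow the denominator sentence or the population sentence, and the two can give different rates. A subject with failed mapping, or with no histology-confirmed node, is in the denominator under the first and absent under the second. Excluding such subjects from a detection rate takes out the cases in which detection failed.

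At stake are the two absolute per-subject rates, that is, how often each method finds a node in a patient. This is the only per-subject effectiveness measure visible in this copy; the text of 14.5 (Other Analyses) and 14.7 (Handling of Missing Data) is not shown. Setting PP beside mITT would not reveal the problem, because both lose the same subjects. The only visible population that keeps failed mappings is the safety population, which 14.1 assigns to safety endpoints.

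**Working it through.** **The plan's own figure.** No number is stated for the per-subject endpoint. The nearest is the PP allowance in 14.8: 356 / (1 − 0.06) = 378.7, rounded up to 379 nodes, which reproduces. At 2 nodes per patient, 379 / 2 = 189.5, in line with the cap of 190 in 7.1. Six percent of 190 is 11.4, so about 11 subjects are allowed for all PP exclusions together.

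**Inputs (assumptions).** A = 190 attempted, taken from the cap. Per-subject rates near 96% and 91.6%, which are the node-level planning rates in 14.8 used as stand-ins. k = attempted subjects with no confirmed node; no value is given, so a range is shown.

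**Formula.** Let D be the number of subjects with a detection. Every one of the k subjects is a non-detection for both methods, so D is unchanged by removing them. The rate over attempted subjects is D/A; after removal it is D/(A − k). The excess is D/(A − k) × k/A. Per subject removed this is about 0.96/190 = 0.5 points for IC2000/SPY and 0.916/190 = 0.5 points for Tc99m.

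| k (share of 190) | IC2000/SPY: after removal vs attempted | Excess, points | Tc99m: after removal vs attempted | Excess, points |
|---|---|---|---|---|
| 0 | equal | 0 | equal | 0 |
| 2 (1.1%) | 180/188 = 95.7% vs 180/190 = 94.7% | +1.0 | 172/188 = 91.5% vs 172/190 = 90.5% | +1.0 |
| 4 (2.1%) | 179/186 = 96.2% vs 179/190 = 94.2% | +2.0 | 170/186 = 91.4% vs 170/190 = 89.5% | +1.9 |
| 6 (3.2%) | 177/184 = 96.2% vs 177/190 = 93.2% | +3.0 | 169/184 = 91.8% vs 169/190 = 88.9% | +2.9 |
| 11 (5.8%) | 172/179 = 96.1% vs 172/190 = 90.5% | +5.6 | 164/179 = 91.6% vs 164/190 = 86.3% | +5.3 |

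The last row needs nearly the whole 6% PP allowance to be subjects with no confirmed node. It is an outer limit, not an expectation.

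**Between-method difference.** For k = 11 the difference is 8/179 = 4.47% against 8/190 = 4.21%, a change of 0.26 points. That is the largest change in the table.

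**Rules that act in other directions.**

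- PP drops ineligible and partial-dose subjects. With k = 0, 182/190 = 95.8% attempted, and 11 such subjects dropped who all had nodes found: 171/179 = 95.5%, slightly lower.
- mITT drops aborted mappings. With four aborted and 182/190 = 95.8% over attempted: 178/186 = 95.7% if nodes were found in all four, 182/186 = 97.8% if in none.
- mITT keeps palpation-only subjects. Let u of these never have been mapped, so that they fall outside the attempted denominator. With 190 enrolled and k = 4:
  - u = 0: 179/186 = 96.2% vs 179/190 = 94.2%, +2.0 points.
  - u = 2: 177/186 = 95.2% vs 177/188 = 94.1%, +1.0.
  - u = 4: 175/186 = 94.1% in both, 0.
  - u = 6: 173/186 = 93.0% vs 173/184 = 94.0%, −1.0.

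**The case against.** The denominator is explicit and stated twice, and 2.6 names no population. Read with the numerator, it already counts failed mappings as non-detections. The conflict rests on one sentence, which may be misplaced: 14.1 reserves mITT for the primary endpoint, and 14.3 has no mITT sentence of its own. This is plausible, and it is why the point is minor. It does not remove the conflict, since the sentence sits directly under this endpoint and names sets that cannot hold the stated denominator.

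The effect may also be small. The table in 14.8 leaves 1 − 0.883 − 0.112 = 0.005 of nodes missed by both methods. Carried over to subjects, that is 0.005 × 190 = 0.95, about one subject and about +0.5 points. It is a node-level figure and not a failed-mapping rate, but neither are the planning rates borrowed above, and it does suggest the low end of the range.

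A reader might infer that analysis in PP or mITT must overstate both rates. The documents do not support that. Only the exclusion of failed mappings and of subjects without a confirmed node has a certain direction; the other rules can offset or reverse it. Whether palpation-only subjects were never mapped, or were mapped without signal, is not settled either. PP counts clinically suspicious nodes as successful mapping, so some of them may be in PP as well.

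A reader might also infer that the non-inferiority result is compromised. That is not shown. The denominator in 14.3 consists of histology-confirmed nodes, and a subject with none contributes nothing to it.

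**Conclusion.** Wrong as written; minor severity. The stated denominator and the populations attached to it in 14.4 cannot both be followed once any attempted subject has failed mapping or no confirmed node. Removing those subjects raises both absolute rates by about 0.5 points each, assuming 190 attempted and rates near the planning values: about 1 point for two subjects and 2 for four, and nothing if there are none. The net direction in PP or mITT as defined is uncertain. The endpoint carries no test, margin or alpha. The conclusion is conditional on the visible text, since 14.5 or 14.7 might bear on it; the wording of 14.1 and 14.4 would still need to be reconciled.

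**What to change.** In 14.4, state that the mapping-attempted denominator governs the per-subject endpoint, and define it: enrolled subjects given both agents in whom mapping was started. State that failed mapping, or no histology-confirmed node, counts as non-detection for both methods.

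If the PP/mITT sentence was meant for the primary endpoint, move it to 14.3. If not, label the PP and mITT per-subject rates as supportive, report how many subjects each set removes, and reconcile this use with the purpose of mITT given in 14.1.

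The cost is wording and one population flag; failed mapping is already to be documented. Sample size, alpha and the primary analysis are unchanged. The downside is that the reported rates may be slightly lower.

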14.5 Other Analyses

14.6 Safety Objective

Safety variables will be documented and summarized for all subjects in the safety analysis population. Safety variables will include all AEs and ADEs, concomitant medications, vital signs and blood loss assessments.

AEs will be graded using the National Cancer Institute Common Terminology Criteria for Adverse Events (NCI CTCAE) and coded using MedDRA. AEs and ADEs occurring during the study will be summarized descriptively with the total number of AEs and ADEs as well as the number and percentage of subjects experiencing AEs and ADEs, overall and by system organ class and preferred term.

Associated AEs that investigators suspect are related to study treatment will also be summarized. Summary of each type of event will be prepared by severity and for all severities combined.

14.7 Handling of Missing Data

14.8 Sample Size Considerations

This is a single arm, non-inferior, sequential design, paired comparison study of IC2000 and SPY with the standard of care, Tc99m/Gamma Probe in the identification of lymph nodes during lymphatic mapping and sentinel lymph node biopsy. The sample size calculation for the primary endpoint was performed using nQuery Advisor® 7.0 (Copyright® 1995-2007, Statistical Solutions Ltd). To support the sample size calculation, the average LN detection rate with IC2000 and SPY (Q_T) of 96% was assumed, based on the recent meta-analyses; Mok et al. 56 An average detection rate of 91.6% has been assumed for Tc99m and Gamma Probe (Q_C) 57 A 5% non-inferiority margin is deemed to be conservative for sentinel lymph node biopsy (SLNB).

Assuming an average of 2 excised LNs per patient evaluated by both methodologies with 11.2% discordance $\frac{57}{1}$, 137 subjects would be required to prove the non-inferiority of IC2000 and SPY with a non-inferiority margin of 5% using a one-sided 2.5% alpha and 90% power. A 1.0% Q_T advantage would establish non-inferiority.

Lower one-sided 97.5% confidence bound: Difference in paired proportions (simulation)

	90% Power	1-sided p=0.025
Confidence level, 1-α (one-sided)	0.975	0.975
Expected difference, $Q_T - Q_C$, Δ	0.044	0.01
Proportion discordant, $d = q_{10} + q_{01}$	0.112	0.112
Proportion both yes, q ₁₁	0.883	0.883
Lower limit for Q _T - Q _C , LL	-0.050	-0.050
Number of simulations	1000	1000
Random seed for simulations	123	123
Power (%)	90	NA
n (number of paired evaluations)	137	137

Based on a 2-level hierarchical model in which nodes are nested within subjects, and given that we expect an average of 2 nodes to be excised per patient the aforementioned sample size needs to be multiplied by an inflation factor (IF), aka Design Effect (DEFF $\frac{54,55}{}$), of 1+(n-1)*ICC where n is the average sample size per cluster and ICC (expected to be at most 0.1) is the intra-class correlation: IF = 1+ (2x2 – 1) x 0.1 = 1.3, where n was multiplied by 2 due to the fact that LNs will be identified using 2 different methods. Based on a total of 274 LNs and an IF of 1.3, a sample size of 356 lymph nodes will be required. Estimating that 6% of patients will be excluded from the per-protocol (PP) population (see Section 14.1), approximately 379 LNs are required.

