2.8 Sample Size and Statistical Analysis

This is a prospective, open label, multicenter, non-inferiority within-patient study to determine the effectiveness of IC2000 (Indocyanine Green (ICG) for Injection) and the SPY Portable Handheld Imaging System (SPY-PHI) as an intraoperative fluorescence visualization tool, in the visual identification of lymphatic vessels and LNs including LNs during lymphatic mapping and SLNB procedures as confirmed by Tc99m and Gamma Probe. A sample size of 356 LNs contributed by approximately 137 evaluable patients will be required using the following assumptions:

- 1. The average detection rate with Tc99m and Gamma Probe will be 91.6%.
- The average detection rate with IC2000 and SPY will be 96%.
- A power of 90%.
- 4. A non-inferiority margin of 5 percentile units.
- An average of 2 LNs is expected to be excised per patient.

Estimating that 6% of patients will be excluded from the per-protocol (PP) population (see section 14.1), approximately 379 LNs are required.

Additional details are included in Section 14.7, Sample Size Considerations.

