14.3 Primary Objective

To assess the effectiveness of IC2000/SPY during lymphatic mapping and sentinel lymph node biopsy, the proportion of excised lymph nodes identified by IC2000/SPY in-vivo and confirmed by histology (\mathbf{Q}_{T}) will be compared with the proportion of excised lymph nodes identified with Tc99m/Gamma and confirmed by histology (\mathbf{Q}_{C}). The denominator for both \mathbf{Q}_{T} and \mathbf{Q}_{C} will be the total number of lymph nodes identified and excised that were confirmed by histology, inclusive of clinically suspicious lymph nodes.

The following hypothesis will be tested at the lymph node level:

H0:
$$Q_T \le Q_C - 0.05$$
 H1: $Q_T > Q_C - 0.05$

To test this hypothesis, the difference \mathbf{Q}_{T} - \mathbf{Q}_{C} will be calculated and the associated two-sided 95% confidence interval. If the lower bound of the interval is greater than -0.05, non-inferiority (using the PP population) will be claimed.

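### Section 14.8 treats 137 lymph-node pairs as 137 subjects, so the planned 356 nodes carry over 99% power, not 90%, and section 2.8 gives a patient count that cannot supply them

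*Combined protocol and SAP*

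**What the plan says.** Section 14.8 assumes detection rates of 96% for IC2000/SPY and 91.6% for Tc99m/gamma probe, 11.2% discordance, a 5-point margin, one-sided alpha of 2.5% and 90% power. From these it states that "137 subjects would be required to prove the non-inferiority of IC2000 and SPY". The nQuery table below that sentence shows the same 137 in a row whose label begins "n (number of paired evaluations".

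The section then sets an inflation factor of 1 + (2×2 − 1) × 0.1 = 1.3. It explains the cluster size of 4 as follows: "where n was multiplied by 2 due to the fact that LNs will be identified using 2 different methods". It continues: "Based on a total of 274 LNs and an IF of 1.3, a sample size of 356 lymph nodes will be required". An allowance for 6% exclusions from the per-protocol population brings the target to 379 nodes.

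On the unit of analysis, section 14.3 says: "The following hypothesis will be tested at the lymph node level".

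Section 2.8 summarises the plan as "A sample size of 356 LNs contributed by approximately 137 evaluable patients will be required", lists 90% power among the assumptions for that size, and in the same list states: "An average of 2 LNs is expected to be excised per patient". Section 7.1 caps enrolment at 190 subjects.

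**The concern.** One number carries two units within section 14.8. If a pair is one node read by both methods, 137 is already a node count, and doubling it before inflating builds in a factor of two that the 90% power target does not call for. The inflation factor adds a second problem. A paired analysis already accounts for the two readings of each node through the discordance, so the readings should not also be counted as cluster members. Section 2.8 adds a third: 356 nodes from 137 patients is 2.6 per patient, against the stated average of 2.

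Sections 2.8 and 14.8 are where an ethics board, a monitoring board or a regulator looks to see why this many patients receive an investigational injection. If the error stands, the stated power does not describe the planned size, and the summary gives an evaluable-patient number that cannot supply its own node target at the stated yield.

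**Working it through.** **Inputs (sections 14.3 and 14.8).** Expected difference Δ = 0.96 − 0.916 = 0.044; discordance d = 0.112; margin 0.05; one-sided 2.5% (z = 1.96); 2 nodes per patient; ICC at most 0.1. The implied discordant cells are q10 = (0.112 + 0.044)/2 = 0.078 and q01 = (0.112 − 0.044)/2 = 0.034.

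**Formula.** For n node pairs and inflation factor F,

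Power = Φ( (Δ + 0.05) / √[(d − Δ²) F / n] − 1.96 ), with d − Δ² = 0.112 − 0.001936 = 0.110064.

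**Step 1: reproduce the plan's 137.** With n = 137 and F = 1, the standard error is √(0.110064/137) = 0.0283. Then 0.094/0.0283 = 3.32, and Φ(3.32 − 1.96) = 91.3%. Simulation at 137 pairs gives 92.6% with a Wald limit, 90.2% with the Tango score limit and 90.1% with the Newcombe paired limit. The closed-form Wald size for 90% is 131, close to 137. The table's second column fits too: at an observed +0.01 with 137 pairs, the lower limit is 0.01 − 1.96 × √(0.1119/137) = −0.046, just inside −0.05. So 137 node pairs give the stated 90% with no doubling.

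**Step 2: the inflation factor.** The plan's formula is 1 + (n − 1) × ICC, with n the average cluster size and nodes nested in subjects. With 2 nodes per patient and ICC 0.1 it gives 1 + (2 − 1) × 0.1 = 1.1. The plan's 1.3 comes from a cluster size of 4, which counts each node once per method.

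**Step 3: power at the planned size.**

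| Nodes | F = 1.1 | F = 1.3 |
|---|---|---|
| 274 (137 patients × 2) | 99.4% | 98.4% |
| 356 (planned) | 99.9% | 99.7% |

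A simulation of 178 patients with 2 nodes each and a cluster-robust lower limit agrees: 99.9% at a design effect of 1.1 and 99.7% at 1.3.

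**Step 4: the size that 90% power needs.** Inflating once gives 137 × 1.1 = 150.7, or 151 nodes, up to 137 × 1.3 = 178.1, or about 178 nodes. The planned 356 is therefore 356/178 = 2.0 to 356/151 = 2.4 times that size.

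**Step 5: patients in section 2.8.**

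- 356/137 = 2.6 nodes per patient, against the stated 2.
- 137 × 2 = 274 nodes, not 356.
- 356/2 = 178 patients, which is 41 more than 137.
- With 6% exclusions, 178/0.94 = 189.4 patients. Equivalently, 356/0.94 = 378.7, or 379 nodes, and 379/2 = 189.5. Both match the cap of 190 in section 7.1.

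The node targets and the cap agree with each other. The figure that does not fit is the 137 evaluable patients, apparently the pre-inflation number carried over.

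**The case against.** The best case for leaving this alone is that nothing is harmed. The trial is oversized, the decision rule in section 14.3 is unaffected, and the node targets and cap agree. The high power also exists only at the assumed +4.4-point advantage. With discordance held at 11.2% (an assumption), 356 nodes give about 84% to 90% power at +1 point and 70% to 77% at no difference, so the extra size may be useful. All of this is true, and it is why the planned size should not change. But neither section presents the extra nodes as a safeguard.

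Four narrower points deserve weight.

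- **Where 90% is claimed.** Section 14.8 attaches it to the base of 137; section 2.8 attaches it to 356 nodes. The misstatement of power lies in 2.8.
- **The unit of a pair.** The table does not name it, and the source cited for the 91.6% and the 11.2% cannot be consulted here. The node reading is partly an inference. It rests on the 96% being described as a node detection rate, on the text speaking of nodes assessed by both methods, and on the node-level test.
- **The factor of 1.1.** It assumes exactly 2 nodes in every patient. For an assumed coefficient of variation of 0.5 to 0.7 in node counts, the usual correction gives about 1.15 to 1.20, at which power at 356 nodes still exceeds 99.8%. With 2 nodes per patient, 1.3 needs an ICC of 0.3, above the plan's stated maximum.
- **The figure of 178.** Section 8.1 is incomplete in the public copy and may state a patient target. The 178 is what 356/2 implies, and the sponsor should confirm it. The conflict inside 2.8 remains either way.

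**Conclusion.** The concern holds. Under the plan's own rates, discordance, margin and alpha, 356 nodes have 99.7% power (factor 1.3) to 99.9% (factor 1.1), against the 90% given in section 2.8. That section's evaluable-patient count is 41 below what its node target needs at 2 nodes per patient. The stated reason for the factor of 1.3 is wrong, although its value is conservative.

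This is an error of reporting and reconciliation, worth correcting because both sections justify the size of the trial. It does not underpower the study: even 274 nodes give 98.4% to 99.4%. The conclusion rests on the +4.4-point difference and 11.2% discordance, and on a pair being one node. The plan claims no power at equal performance. There the answer depends on a discordance that has to be assumed: for 6.8% (both cells 0.034) to 15.6% (both cells 0.078), power at 356 nodes runs from 93% down to 62% with factor 1.1, and from 89% down to 55% with factor 1.3.

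**What to change.** Change the wording of sections 14.8 and 2.8 only.

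1. In 14.8, describe 137 as paired lymph-node evaluations, not subjects.
2. Remove the two-methods reason for the cluster size. Either use 1.1, with its assumption of 2 nodes per patient and ICC 0.1, or keep 1.3 and call it a cushion. Keeping 1.3 is the safer choice if node counts vary between patients.
3. State the power at 356 nodes as above 99% at +4.4 points and 11.2% discordance. If the extra nodes are meant as protection against a smaller advantage, say so. Any power quoted at equal performance should be a range over stated discordance values, not a single figure.
4. In 2.8, replace about 137 evaluable patients with 178 (about 190 enrolled), subject to the sponsor's confirmation.
5. Note that the 1.0% advantage quoted in 14.8 was computed at 137 pairs. No new threshold is needed.

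The cost is the redrafting of two sections. The node targets, enrolment cap, procedures, analysis and decision rule stay as they are.
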